6.3.7 Removal of subjects

Participants will be prematurely discontinued from the study if any of the following occurs:

- The participant withdraws consent
- The participant is lost to follow-up
- The participant experiences an untoward event that warrants discontinuation from the study
- The participant develops a health problem and needs treatment that would affect the results of this study
- The study is cancelled for other administrative reasons
- Death of the participant

At the time of premature discontinuation, an off- study form will be completed and no further data collection will occur. Data through the time of enrollment and premature discontinuation will still be used for study purposes.

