Randomized double blinded placebo-controlled trial. There will be a total of 60 participants, with 20 participants with endometriosis randomized to the placebo group, 20 participants with endometriosis randomized to the letrozole group and 20 control patients with no history of endometriosis. Letrozole and placebo medication will be started on the first day of gonadotropin injections and continued until the day of trigger shot. Medication will be restarted the night of egg retrieval and continued for 2 weeks post retrieval. Endometriosis associated symptoms will be evaluated using a survey modeled after the clinical survey developed by the World Endometriosis Research Foundation Endometriosis Phenome and Biobanking Harmonisation Project. Surveys will be administered at baseline ultrasound appointment for controlled ovarian hyperstimulation cycle, the day of trigger shot, 3 weeks following egg retrieval, 6 weeks following egg retrieval and 12 weeks following egg retrieval.

Study Population

Reproductive age women with a prior diagnosis of endometriosis, who are undergoing controlled ovarian stimulation.

Number of Participants

A total of 60 participants (20 in each of the primary comparison groups) as well as an additional 20 age matched controls without a history of endometriosis will be enrolled. Enrollment will occur over a 12-month period, from April 2019 to April 2020.

Number of Study Sites

There is a single study site for this trial. All participants will be recruited, and all study related activities will be completed, at the University of California San Francisco Center for Reproductive Health.

Table of Contents

1 - Introduction	10
1.1 Introductory Statement	10
2 - Background	11
2.1.1 Preclinical Experience.....	11
2.1.2 Clinical Experience.....	11
2.2 Background/prevalence of research topic	11
3 - Rationale/Significance.....	12
3.1 Problem Statement.....	12
3.2 Purpose of Study/Potential Impact	12
3.3.1 Potential Risks	12
3.3.2 Potential Benefits	13
4 - Study Objectives	14
4.1 Hypothesis	14
4.2 Primary Objective	14
4.3 Secondary Objectives (if applicable)	14
5 - Study Design.....	15
5.1 General Design Description.....	15
5.1.1 Study Date Range and Duration	15
5.1.2 Number of Study Sites	15
5.2.1 Primary Outcome Variables	15
5.2.2 Secondary and Exploratory Outcome Variables (if applicable).....	15
5.3 Study Population.....	15
5.3.1 Number of Participants.....	16
5.3.2 Eligibility Criteria/Vulnerable Populations.....	16
6 - Methods	17

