6.2 Assessments

Endometriosis associated symptoms will be evaluated using a survey modeled after the clinical survey developed by the World Endometriosis Research Foundation Endometriosis Phenome and Biobanking Harmonisation Project [10]. The survey will use a visual analog scale (VAS) to quantify pain and symptoms experienced by participants. Participants will complete this survey at their baseline ultrasound appointment for their controlled ovarian hyperstimulation cycle, the day of trigger shot, 3 weeks following egg retrieval, 6 weeks following egg retrieval and 12 weeks following egg retrieval if not pregnant. The first survey will include questions regarding any recent or prior medical or surgical treatment of their

endometriosis. It will also assess baseline use of pain medications for their endometriosis-associated pain. Study participants will be allowed to take acetaminophen when needed (Tylenol, 650 mg tablet) for pain control, but asked to record the number of tablets used.

Secondary outcomes looking at egg and embryo quality and quantity will be assessed using standard embryologists evaluation and grading of all eggs and embryos collected during controlled ovarian hyperstimulation at the University of California Center for Reproductive Health. Embryologist will be blinded to the study participants' assignments to either placebo or control group.

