6.3.1 Study Schedule

M.D. Visit	
 • M.D. to identify patient as potential study participant • M.D. discusses study with patient • M.D. to notify study team if patient interested
Meet Study Team	
 • Discuss study with patient and answer questions • Subject signs study and HIPPA consents • Randomization completed, patient provided medication
Baseline Ultrasound	
 • Completion of survey #1
Stimulation Monitoring	
 • Daily letrozole/placebo starting with first day of stimulation medications • Routine uterine and ovarian ultrasound monitoring every 1-3 days at UCSF CRH • Routine blood draws for hormonal assessment every 1-3 days at UCSF CRH (patients and providers blinded to estradiol levels)
Trigger Shot	
 • Based on routine trigger shot parameters, including mean diameter of largest follicles • Completion of survey #2 • Discontinuation of letrozole/placebo
Oocyte Retrieval	
 • Retrieve all visible follicles • Follicular fluid obtained for hormonal evaluation • Restart letrozole/placebo evening of retrieval and continue daily for 2 weeks
Embryology Lab	
 • Count total number of retrieved oocytes • Count mature oocytes and fertilization rate (if making embryos) • Assess embryo quality using UCSF CRH standard grading criteria

3 Weeks Post Retrieval	
 Completion of survey #3
6 Weeks Post Retrieval	
 Completion of survey #4
12 Weeks Post Retrieval	
 Evaluation of pregnancy status Completion of survey #5
Long-term Follow-up	
 Medical record review for pregnancy outcomes of transferred embryos and additional endometriosis treatment.

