6.4.1 Statistical Design

An intention-to-treat analysis of the results will be used, meaning results of the study will be based on the initial treatment assignment and not the treatment eventually received. The primary outcome will be assessed by changes in pain survey scores before, during and following controlled ovarian hyperstimulation.

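### Section 6.3.7 stops all data collection for participants removed for a health problem needing result-altering treatment or for an untoward event, so later pain scores that the analysis by assignment in 6.4.1 needs are never collected

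*Combined protocol and SAP*

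**What the plan says.** **Removal.** Section 6.3.7 lists six reasons for premature discontinuation from the study. Four are withdrawal of consent, loss to follow-up, death and cancellation of the study. The other two depend on the participant's clinical course: an untoward event that warrants discontinuation, and "The participant develops a health problem and needs treatment that would affect the results of this study". After any of the six, "no further data collection will occur". Data gathered before removal remain in use.

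**Analysis.** Section 6.4.1 adopts intention-to-treat, so that "results of the study will be based on the initial treatment assignment and not the treatment eventually received". Section 5.2.1 puts the primary pain comparison at baseline and at 6 and 12 weeks after retrieval.

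**Missing data.** Section 6.4.5 will try to separate data missing at random from data missing in relation to letrozole use. It allows multiple imputation in the first case and calls for sensitivity analyses with non-ignorable models if missing at random is implausible.

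**Week-12 survey.** Section 6.2 schedules the last survey at "12 weeks following egg retrieval if not pregnant". The Synopsis (Study Design) lists "6 weeks following egg retrieval and 12 weeks following egg retrieval" without that limit. The schedule in 6.3.1 puts "Evaluation of pregnancy status" and "Completion of survey #5" together at week 12. Sections 6.3.5 and 7.9 have participants complete the surveys with no mention of pregnancy.

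**The concern.** Analysis by assignment needs outcomes from women whose treatment changed as well as from those whose treatment did not. The two clinical-course triggers in 6.3.7 stop collection for some of those women. One of them selects on the very ground that the new treatment would affect the results. If removal comes before week 6 or week 12, the primary scores from then on do not exist.

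Two comparisons would then rest on the retained women or on a model for the rest: the change in pain after stimulation, and the letrozole-placebo contrast. With 20 women per group, a few selective losses can matter.

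The week-12 survey raises a smaller question of the same kind. If 6.2 is followed, the week-12 comparison is limited to a group defined after randomisation. Pregnancy is also an outcome compared between groups (5.2.2).

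**Working it through.** **1. The plan's own figure.** Inputs from 6.4.2 and 6.4.3.1 are a difference of 3 points, SD 2.5, power 0.90, significance level 0.05 (two-sided assumed) and 20% dropout. The standardised difference is 3/2.5 = 1.2. The two-sample t-test needs 15.6, so 16 per group, and 16/0.8 = 20 per group. This reproduces the stated 40. At 16 per group the power is 90.7%. The allowance protects power; it does nothing about which women are lost.

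**2. The sections side by side.**

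| Question | 6.3.7 | Elsewhere |
|---|---|---|
| Are removed women left out of the analysis? | No; earlier data are used | 6.4.1: analysed by assigned group |
| Are their later scores available? | No | 6.4.1 implies they are wanted; 5.2.1 makes weeks 6 and 12 primary |
| Does the trigger include treatment for worsening endometriosis pain? | Not stated | 6.2: "Study participants will be allowed to take acetaminophen when needed", with tablets recorded, so simple analgesia is handled on study |
| Does chart review of later endometriosis treatment continue? | Read literally, no | 5.1.1 and 6.3.5 plan it and make no exception for removed women |

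**3. Scale in one arm (assumed inputs).** Let m of 20 women be removed, and let their uncollected scores average d points away from the retained mean. Then

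mean of all 20 = retained mean + (m/20) × d,

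so the retained-only mean is off by (m/20) × d.

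| m | d = 1 | d = 2 | d = 3 |
|---|---|---|---|
| 1 | 0.05 | 0.10 | 0.15 |
| 2 | 0.10 | 0.20 | 0.30 |
| 4 | 0.20 | 0.40 | 0.60 |

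Here m = 4 uses up the whole 20% dropout allowance, and d may have either sign. The standard error of the arm difference is 2.5 × √(2/n), which is 0.79 at n = 20 and 0.88 at n = 16.

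**4. Between arms.** With P for placebo and L for letrozole, the error is (m_P × d_P − m_L × d_L)/20. It cancels if the arms behave alike. Its extreme in this range is (4 × 3 + 4 × 3)/20 = 1.2 points, which needs four removals in each arm with opposite signs.

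**5. Why no direction is claimed.** Take one assumed scenario. Without other treatment, change is normal with SD 2.5 and mean 3 on placebo and 0 on letrozole. The log-odds of removal rise by 0.5 per point, and 10% are removed overall. Removal is then 15.3% on placebo and 4.7% on letrozole, and the retained-only difference is 2.735. If the new treatment lowers removed women's scores by k points, the difference with every score collected is 3 − 0.1065k.

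| k | All collected | Retained-only minus all collected |
|---|---|---|
| 0 | 3.000 | −0.265 |
| 2 | 2.787 | −0.052 |
| 4 | 2.574 | +0.161 |

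The sign changes at k = 0.265/0.1065, about 2.5. With slopes of 0.25 and 1.0 it changes at about 1.5 and 3.4. The sign depends on a quantity that the documents do not give.

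**The case against.** A reader might infer that 6.3.7 contradicts intention-to-treat or drops women from the analysis. It does neither. Section 6.4.1 sets a rule for analysis, 6.3.7 keeps data up to removal, and those data can be analysed by assigned group. What remains is that the later scores are missing by design.

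A reader might also infer that women are removed because their pain worsens. The trigger requires that she develops a health problem and needs result-altering treatment. That may mean a new, unrelated condition, and acetaminophen is allowed on study. Treatment for endometriosis pain is a possible reading, not a stated one.

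Nor does simply stopping the capsules end follow-up: it is not among the six triggers.

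Section 6.4.5 deserves credit. It foresees missingness related to letrozole and commits to non-ignorable sensitivity models where needed. These models rest on untestable assumptions and cannot replace observed scores. Section 7.12 also foresees a withdrawn participant returning for monitoring of adverse effects, so contact after leaving is not ruled out.

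It can fairly be argued that scores after another effective treatment no longer measure the effect of stimulation. That is a real choice of target. Collecting the scores leaves both analyses open, whereas not collecting them closes one.

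On the week-12 survey, the schedule in 6.3.1 could be read as a pregnancy check before the survey, which would fit 6.2. Sections 6.3.5 and 7.9 state no condition, and 3.3.2 pays for survey 5 without one.

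**Conclusion.** The point holds as a cheap improvement. Under 6.3.7 as written, pain scores after removal for either clinical-course trigger are not collected, including weeks 6 and 12 if removal comes first. The reason for the loss may relate to outcome or arm. That weakens the analysis that 6.4.1 promises without contradicting it.

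No size or direction of bias follows from the documents, which give no removal rate. Under the assumed ranges the one-arm error is 0.05 to 0.60 points, below one standard error. The 1.2-point extreme exceeds one standard error but needs both arms to use the full allowance with opposite signs. The inference that removal would dilute, or inflate, the letrozole effect is not supported, because the sign turns on how much the new treatment changes scores. The planned sample size is not in question.

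The week-12 inconsistency is real but minor. Eligibility (5.3.2) asks for a plan to freeze all oocytes or embryos before transfer, so few women may be pregnant by then, although no rate is given. The 6.2 condition does not touch week 6.

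**What to change.** These changes concern data collection and analysis only; no clinical rule is proposed.

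1. In 6.3.7, limit the end of data collection to withdrawal of consent, loss to follow-up, death and study cancellation.
2. For the health-problem and untoward-event triggers, keep sending the scheduled electronic surveys to participants who still consent. Record the date and type of any new treatment.
3. State whether treatment for worsening endometriosis pain falls under the health-problem trigger, and whether chart review continues after removal.
4. In 6.4, make the main analysis use all collected scores by assigned group. Add a sensitivity analysis that treats scores after new treatment as missing, using the models foreseen in 6.4.5.
5. Reconcile 6.2 with the Synopsis, 6.3.1, 6.3.5 and 7.9 on the week-12 survey. Collecting survey 5 from all women with pregnancy status recorded is preferable, since week 12 is a primary time point.

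The cost is a short amendment, because the surveys are already electronic and scheduled. The downside is that some scores will reflect other treatment or pregnancy and may shrink the observed difference. Analysis by assignment already accepts this.

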6.4.1 Statistical Design

An intention-to-treat analysis of the results will be used, meaning results of the study will be based on the initial treatment assignment and not the treatment eventually received. The primary outcome will be assessed by changes in pain survey scores before, during and following controlled ovarian hyperstimulation.

6.4.2 Sample Size Considerations

Primary Outcome: change in endometriosis-related pain score pre and post controlled ovarian hyperstimulation.

Test: two sample test.

1:1 randomization powered at 0.9 to detect a 3-point difference on the VAS pain scale.

A standard deviation of 2.5 was used, based on previous literature [11].

The effect size of 3 was based on review of the literature which supports the most accurate evaluation of endometriosis related pain using a visual acuity scale. Using this scale, a change in 3 points typically results in change in pain category (mild, moderate, severe) and therefore represents a clinically significant reduction or increase in symptoms.

Sample Size Estimate: A total of 40 participants (20 in each of the primary comparison groups) would provide 90% power to detect a change in pain score of 3 between the two groups. This accounts for an estimated study participant dropout rate of 20%.

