4.1 Hypothesis

Null hypotheses:

- a) Ovarian hyperstimulation has no impact on endometriosis-related symptoms.
- b) The use of letrozole during ovarian hyperstimulation has no impact on endometriosis-related symptoms.
- c) The use of letrozole during ovarian hyperstimulation has no impact on egg/embryo quantity or quality.
- d) The use of letrozole during ovarian hyperstimulation has no impact on pregnancy rates.

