4.2 Primary Objective

To evaluate the impact of ovarian hyperstimulation on endometriosis-related symptoms.

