4.3 Secondary Objectives (if applicable)

To evaluate the impact of letrozole use during ovarian hyperstimulation with respect to endometriosis-related symptoms, embryo/egg quality and quantity and pregnancy rates.

5 - Study Design

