5.2.1 Primary Outcome Variables

- To compare the mean endometriosis pain score at baseline, 6 and 12 weeks following egg retrieval.
- To evaluate how endometriosis pain scores change throughout controlled ovarian hyperstimulation.

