6.4.3.1 Primary Analyses

Statistical analysis will be performed using Stata versions 14 (Stata Corp., College Station, TX) and under the guidance of a statistician. A univariate analysis will be performed to compare patient cycle characteristics between the patient groups. Cycle characteristics of interest will include: patient age, number of prior stimulations, most recent treatment for endometriosis, presence of an endometrioma, number of stimulation days, number of follicles 13mm+ and 10-12mm, number of retrieved oocytes, number of mature oocytes.

For continuous data, including evaluation of pain scores, a two-sample t-test or Wilcoxon rank sum will be used as appropriate. All tests will be performed at the 0.05 level of significance.

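### The primary objective is a before/after change in pain, but the only test named is two-sample and the only power statement is for letrozole versus placebo, a secondary objective

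*Combined protocol and SAP*

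**What the plan says.** The primary question is posed as a change over time within women:

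- Section 4.1, null hypothesis (a): "Ovarian hyperstimulation has no impact on endometriosis-related symptoms".
- Section 4.2: "To evaluate the impact of ovarian hyperstimulation on endometriosis-related symptoms".
- Section 5.2.1: "To compare the mean endometriosis pain score at baseline, 6 and 12 weeks following egg retrieval", and also how pain evolves during stimulation.
- Section 6.4.1: "The primary outcome will be assessed by changes in pain survey scores before, during and following controlled ovarian hyperstimulation".
- The opening line of section 6.4.2 also describes the primary outcome as a pre/post change.

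The letrozole question is secondary. Section 4.3 reads "To evaluate the impact of letrozole use during ovarian hyperstimulation with respect to endometriosis-related symptoms", and sections 5.2.2 and 6.4.3.2 list the comparisons of pain between placebo, letrozole and control groups among the secondary outcomes.

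The sample size and the analysis follow the other question. Section 6.4.2 specifies "Test: two sample test" with 1:1 randomisation, and says that 40 women, 20 per group, "would provide 90% power to detect a change in pain score of 3 between the two groups". By section 5.3.1 the only randomised groups are placebo and letrozole. Section 6.4.3.1, headed Primary Analyses, says: "For continuous data, including evaluation of pain scores, a two-sample t-test or Wilcoxon rank sum will be used as appropriate". No paired test, signed-rank test, repeated-measures analysis or mixed model is named anywhere, and there is no other power statement.

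**The concern.** Section 6.1.2 gives every participant, controls included, her usual stimulation. Stimulation is therefore constant across the groups. Letrozole versus placebo estimates a drug effect. Endometriosis versus control estimates a difference in change between two populations. Neither can show a change that all groups share, and that shared change is what hypothesis (a) is about. The remaining literal reading is to apply the two-sample test to baseline and follow-up scores from the same women, which ignores the pairing.

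Two misreadings could follow. A between-group result of no difference could be reported as no effect of stimulation when pain rose equally everywhere. Alternatively, a letrozole result could be presented as the answer to the primary objective, with a 90% power figure that was calculated for a different question.

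The plan also names no single primary contrast. Weeks 6 and 12 and the course during stimulation all stand as primary, each tested at 0.05, and nothing says which arms enter the before/after comparison.

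**Working it through.** **Inputs.** From section 6.4.2: difference 3 points, SD 2.5, power 0.90, dropout 20%, 20 per group. From section 6.4.3.1: alpha 0.05. Assumed: two-sided testing, and a correlation ρ between visits of 0, 0.3, 0.5 or 0.7, because the plan gives none. The plan does not say whether 2.5 is the SD of a single score or of a change.

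**1. Reproduce the plan's figure.** For a two-sample t-test the noncentrality is 3 / (2.5 × √(2/n)). At n = 15 per arm power is 88.7%; at n = 16 it is 90.7% (noncentrality 3.39). Then 16 / (1 − 0.20) = 20 per arm, 40 in total. The stated number reproduces exactly, as a comparison of two independent arms.

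**2. What that test does for hypothesis (a).** If pain rises by 3 points in both arms, the true between-arm difference is 0, and the test rejects only at its 5% error rate.

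**3. What the before/after question would have.** If 2.5 is a single-visit SD, the SD of change is 2.5 × √(2(1 − ρ)). A paired t-test on the 16 placebo completers has noncentrality 3 / (SD of change / √16). At ρ = 0.5, for example, the SD of change is 2.50 and the noncentrality is 3 / (2.50/4) = 4.8.

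| ρ | SD of change | Paired power, 3 points, n = 16 | Change detectable at 90% power | Letrozole vs placebo on change, 16 per arm | Letrozole vs placebo, follow-up adjusted for baseline |
|---|---|---|---|---|---|
| 0 | 3.54 | 0.89 | 3.1 | 0.64 | 0.90 |
| 0.3 | 2.96 | 0.97 | 2.6 | 0.79 | 0.92 |
| 0.5 | 2.50 | 0.99 | 2.2 | 0.91 | 0.96 |
| 0.7 | 1.94 | >0.99 | 1.7 | 0.99 | 0.99 |

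The last column is simulated with 16 per arm and single-visit SD 2.5; its type I error was 4.9% to 5.1%. The 90% claimed for letrozole versus placebo therefore holds if 2.5 is the SD of whatever is analysed. If 2.5 is a single-visit SD and change scores are compared, it does not hold at the lower correlations.

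**4. The literal unpaired reading.** A two-sample test of baseline against follow-up in the same 16 women (simulated, SD 2.5) has true type I error of 4.9%, 2.1%, 0.8% and 0.1% at the four correlations. Its power for 3 points is still 91% to 98%. The damage is a wrong error rate and interval, not a missed 3-point change.

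**5. Several primary contrasts.** Take three of them (trigger day, 6 weeks, 12 weeks), each tested at 0.05, with equal correlations between visits. Correctly sized tests give a familywise error of about 11% to 14%: 12.6% to 12.8% for paired tests, and 14.2% falling to 11.0% for between-arm scores as ρ goes from 0 to 0.7. The unpaired misuse in step 4 gives 13%, 5.6%, 2.2% and 0.3% instead.

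**The case against.** The best counter-argument is that section 6.4.2 is coherent on its own terms. It labels the two groups of 20 as the primary ones to compare, and the synopsis echoes this. A pre/post change examined with a two-sample test is then a between-arm test of change scores, and the arithmetic is right. On that reading letrozole versus placebo was always meant to be primary. The label is real evidence of intent, but it contradicts sections 4.2, 4.3, 5.2.1, 5.2.2 and 6.4.3.2. It shows that the documents disagree about which comparison is primary; it does not resolve the disagreement.

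It can also be said that section 6.4.3.1 gives a general rule for continuous data, to be used as appropriate under a statistician's guidance, and never states that the same women will be compared with an unpaired test. That is fair. The figures in step 4 show the consequence of a literal reading, they lean conservative, and they should not carry the severity. What remains is that the section headed Primary Analyses offers no method for the primary objective.

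A third point is that patient numbers are adequate and that mean pain at each time point will be reported, so a common rise would be visible. Adequacy for 3 points is accepted. A visible mean, however, is not a pre-specified estimate with an interval.

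Finally, sections 6.3.1, 6.3.5 and 7.9 describe the 12-week survey without the restriction to non-pregnant women found in section 6.2. That is a further inconsistency to reconcile, and it does not cancel the explicit restriction.

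**Conclusion.** The concern holds and must be fixed. Objective, test and power statement do not describe the same comparison. The 90% power belongs to letrozole versus placebo, and the before/after objective has no suitable named test, no defined contributing arm, no primary time point and no power statement. The missing power statement should not be read as low power: on the plan's own 3 points, 16 placebo completers give 0.89 or more in a paired analysis across the correlations considered.

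The mismatch itself follows from the text and needs no assumption. The sizes rest on two-sided testing, 16 completers per arm, the assumed correlations and, where stated, 2.5 being a single-visit SD.

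**What to change.** Choose one of two routes and align sections 4, 5.2, 6.4.2 and 6.4.3 with it.

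- **Route A: keep the hyperstimulation objective.** In section 6.4.3.1 specify a paired change from baseline with 95% CI in the placebo arm. Do not pool it with letrozole, since pooling would mix any drug effect into the estimate. Label it a non-randomised before/after estimate. In section 6.4.2 state the change detectable at 90% power with 16 completers: about 1.7 to 3.1 points for an SD of change of 1.94 to 3.54 (2.2 if the SD of change is 2.5).
- **Route B: make letrozole versus placebo the primary objective.** This matches the randomisation and the sample size. Report the before/after change as secondary, with a paired analysis.

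Under either route:

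1. State that the 90% power for 3 points refers to letrozole versus placebo and holds only if 2.5 is the SD of the analysed quantity. If 2.5 is a single-visit SD, adjusting follow-up pain for baseline pain gives about 0.90 to 0.99 over the correlations above.
2. Name one primary time point, and make the others secondary or test them in a fixed order. Under section 6.2 a 12-week primary would lose women who conceive, so that section must be reconciled with sections 6.3.1, 6.3.5 and 7.9 before the choice is made.

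The cost is protocol and SAP wording; the five surveys are already planned, so no patients or data are added. Claims at other time points become secondary and the stated power becomes conditional. Route A leaves the primary result as a before/after estimate; Route B moves the hyperstimulation question to secondary.
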